#### *Follow Up Visit*

The follow up visit takes place approximately one week after the final treatment session. This visit will be completed in person. Adverse events and concomitant medications and therapies will be assessed and recorded. Participants will complete the MOODS-SR, the BIS, the BRIEF-A, the I-7, the SAFTEE, the Delgado gambling task, and Iowa gambling task. The order of administration of the gambling tasks will be randomized. A licensed clinician will administer the C-SSRS and the CGI-S/I.

#### *Communication with participants throughout the study:*

Participants who consent to text messaging, in addition to standard email and phone communication, will receive a text message reminder before every scheduled visit. Text messages will be sent via Updox Secure Text Messaging and SMS. Updox is an online messaging service that specializes in secure healthcare communication.

Participants who consent to text messaging will receive a text message the day before each scheduled study visit. This message will be sent as a SMS text message letting the participant know they have received a secure message from the MGH Photobiomodulation Lab with a link to access the message. The first message received will instruct them to enter in their full name and create a PIN to access the message. Each time a message is received they must enter their unique PIN number to access the message. Study staff do not have access to anyone's personal PIN numbers. Individuals are able to respond back to the message they receive with questions or for more information if necessary.

### **tPBM Administration**

The t-PBM-NIR device used in the study is the Litecure's LightForce® EXPi Deep Tissue Laser Therapy™ System, Transcranial PhotoBioModulation-1000 (tPBM-2.0). The tPBM-2.0 is an investigational device based on LiteCure's LightForce® EXPi Deep Tissue Laser Therapy™ System. For the investigational study, the EXPi System's beam delivery - Empower™, is modified to non-invasively deliver Near-Infrared Radiation (NIR) to subjects diagnosed with Bipolar Disorder. The modified system is also configured to provide sham (placebo) treatment. The device is manufactured and supplied by LiteCure LLC, [name].

The treatment program (using the parameters outlined below) will be programmed into the device. The console displays the time and energy delivered and automatically turns itself off once the treatment is completed.

*Table 1. tPBM Parameters*

| Measure (unit)                           | Value   |
|---|--|
| Wavelength (nm)                                 | 808nm  |
| Exposure time (s)                               | 333  |
| Area of exposure (cm  )             | 24   |
| Irradiance, Power Density (mW/cm  ) | 300  |
| Fluence (J/cm  )                    | 100  |
| Total Energy (kJ)                               | 2.4  |
| NIR Source                                      | Laser  |
| Laser Output (W)                                | 3.5 per fiber (7 total)  |
| Wave Mode                                       | Continuous   |
| Anatomical Targets                              | F4 & F8 (proximity)  |
| Device  | Litecure's LightForce® EXPi Deep Tissue Laser Therapy™ System, Transcranial PhotoBioModulation-1000 (tPBM-2.0) |

The tPBM-2.0 is considered a Class II medical device per 21 CFR 890.5500 and 878.4810 and is manufactured per 21 CFR 820. It utilizes a laser diode source with a maximum continuous (CW) output of  $\leq$ 30 Watts at a wavelength of 808 nanometers (nm) and nominal beam diameter of 40mm at the outside aperture.

The tPBM-2.0 consists of a therapeutic laser console (that produces laser energy as NIR), and an optical delivery system consisting of a flexible, double-sheathed optical fiber connected to a custom helmet (cap). The cap is configured to deliver NIR light to EEG site F4 (or in close proximity if covered by hair), covering a total surface treatment area of approximately 24 cm^2 [12 cm^2 x 2]. It also includes laser safety eye ware with an optical density rating  $>5.0$  at 808 nm.

The therapeutic laser console is the only component of the device that is not MRI compatible. It will be stored in an equipment room located in Zone 2 (area with no detectable magnetic field but to which access is restricted due to scanner proximity). An MRI-compatible optical fiber will connect the laser console to the MRI-compatible cap. The safety eye wear is also MRI compatible.

Aside from the cap, the tPBM-2.0 is the same device as LiteCure's EXPi System – Model LTS-2500, which is marketed under FDA's 510(K) # K107637.

The cap is a custom 3D-printed headgear made of plastic and serves to hold the laser probe in place, between the MRI coil and the subject's head. The cap is provided by the device manufacturer (LiteCure) and is very similar to those used in our previous t-PBM studies. The laser probe (attached to the cap) will be connected to the laser console with a multimode MR-compatible optical fiber. The distal end of the optical fiber is fitted with ceramic ferrules, which will be affixed to the cap. The cap (headgear) contains clamps which secure the ferrules. The cap will be used in place of the wand. The cap is the only modification of the device delivery system, and it was required in order to do the t-PBM inside the MRI scanner. The cap is a component of the tPBM-2.0 device; it is not a separate device. The cap is used to apply NIR to EEG site F4.

The t-PBM-2.0 is a nonsignificant risk device because it:

1. Is NOT intended as an implant and DOES NOT present a potential for serious risk to the health, safety, or welfare of a subject;
2. Is NOT purported or represented to be for a use in supporting or sustaining human life and DOES NOT present a potential for serious risk to the health, safety, or welfare of a subject;
3. Is NOT for a use of substantial importance in diagnosing, curing, mitigating, or treating disease, or otherwise preventing impairment of human health and DOES NOT present a potential for serious risk to the health, safety, or welfare of a subject; or
4. DOES NOT otherwise present a potential for serious risk to the health, safety, or welfare of a subject.

Further,

- The t-PBM-2.0 maximum dose administered in this study does not exceed the Maximum Permissible Exposure (MPE) for skin – Center for Devices and Radiological Health (CDRH), 21CFR1040.10 and 21CFR1040.11;
- The t-PBM-2.0 is substantially equivalent to the OmniLux New U which the FDA has already categorized as a non-significant risk device;
- Currently FDA-cleared lasers are typically available over-the-counter and are considered safe to use without professional supervision.
- The MGB IRB determined a similar PBM device as NSR for the ELATED-3 study (IRB Protocol Number 2016P001490). The ELATED-3 device operated at significantly higher irradiances than the current PBM device. The FDA determined that an IDE was not required for the ELATED-3 device.
- The current PBM device was deemed to be NSR by the NYU Langone Health IRB in previous studies.

The tPBM-2.0 device is currently being used in two other approved studies at MGH: Transcranial Photobiomodulation for Alzheimer's Disease (Protocol #2020p003051) and Transcranial Near Infrared Radiation and Cerebral Blood Flow in Depression (Protocol #2020p000845).

*Safety data from the use of the t-PBM 2.0 device in currently active studies at the time of initial review*

TRIADE (Protocol #2020p000845) – Adverse Events: As of May 4th, 2022, Cumulative data from all three study sites

| Adverse Event                                      | Number Participants | Number Incidences | Severity                            | Study Intervention Relationship  | Resolved                       | Expected        |
|--|---------------------|-------------------|-------------------------------------|--|--------------------------------|-----------------|
|  |                     |                   | Mild= 1
Moderate= 2
Severe= 3 | 1= Not related
2 = Unlikely
3 = Possibly
4 = Probably
5 = Definitely | 1= yes
0= No                | 1= yes
0= no |
| SKIN WARMING                                | 9                   | 12                | 1,1,1,1,1,
1,1,1,1,2,
1,1     | 5,5,3,4,4,
4,4,5,3,5
5,4   | 1,1,1,1,1,
1,1,1,1,1
1,1 | 1               |
| INSOMNIA                                    | 3                   | 4                 | 2,1,2,2                             | 3,4,3,4  | 1,1,1,0                        | 1               |
| EARLY MORNING AWAKENING                     | 1                   | 1                 | 3                                   | 4  | 1                              | 1               |
| DISCOMFORT DURING MRI                       | 2                   | 2                 | 1,2                                 | 5,3  | 1,1                            | 1               |
| PANIC ATTACK DURING MRI                     | 1                   | 1                 | 2                                   | 4  | 1                              | 1               |
| ANXIETY DURING MRI                          | 1                   | 1                 | 1                                   | 1  | 1                              | 1               |
| HEADACHE                                    | 8                   | 8                 | 1,2,1,2,
2,1,2,1                 | 1,3,3,3,
1,1,4,4  | 1,1,1,1,
1,1,1,1            | 1               |
| CLAUSTROPHOBIA                              | 1                   | 1                 | 1                                   | 4  | 1                              | 1               |
| BLURRY VISION                               | 1                   | 1                 | 1                                   | 2  | 1                              | 0               |
| SEIZURE                                     | 1                   | 1                 | 2                                   | 2  | 1                              | 0               |
| PANIC ANXIETY                               | 3                   | 3                 | 1,1,2                               | 4,1,1  | 1,1,1                          | 1,0,1           |
| PAIN ON FOREHEAD                            | 1                   | 1                 | 1                                   | 4  | 1                              | 1               |
| BURNING SENSATION ON SKIN                   | 1                   | 1                 | 2                                   | 5  | 1                              | 1               |
| PANIC ATTACK WITH DISSOCIATION              | 1                   | 1                 | 1                                   | 0  | 1                              | 0               |
| RENAL INFECTION                             | 1                   | 2                 | 3,3                                 | 1,1  | 1,1                            | 0,0             |
| MOTOR VEHICLE ACCIDENT (NO PHYSICAL INJURY) | 1                   | 1                 | 1                                   | 1  | 1                              | 0               |
| NIGHTMARES                                  | 1                   | 1                 | 1                                   | 4  | 1                              | 1               |
| STYE  | 1                   | 1                 | 1                                   | 3  | 1                              | 0               |

Mass General Brigham Institutional Review Board  
Intervention/Interaction Detailed Protocol

---

|                                 |   |   |   |   |   |   |
|---------------------------------|---|---|---|---|---|---|
| WORSENING
ANXIETY    | 1 | 1 | 2 | 2 | 0 | 1 |
| “MIND FOG”
AFTER MRI | 1 | 1 | 1 | 4 | 1 | 1 |

TRAP-AD (Protocol #2020p003051) – Adverse Events: As of May 4th, 2022, Cumulative data from all three study sites

| ADVERSE EVENT                                | NUMBER PARTICIPANT S | NUMBER INCIDENCE S | SEVERITY                            | STUDY INTERVENTION RELATIONSHIP  | RESOLVED                          | EXPECTED                          |
|--|----------------------|--------------------|-------------------------------------|--|-----------------------------------|-----------------------------------|
|  |                      |                    | Mild= 1
Moderate= 2
Severe= 3 | 0= Not related
1 = Unlikely
2 = Possibly
3 = Probably
4 = Definitely | 1= yes
0= No                   | 1= yes
0= no                   |
| ANKLE EDEMA                           | 1                    | 1                  | 3                                   | 0  | 1                                 | 0                                 |
| CHEST TIGHTNESS                       | 1                    | 1                  | 3                                   | 0  | 1                                 | 0                                 |
| DIARRHEA                              | 2                    | 2                  | 1,1                                 | 0,0  | 1,1                               | 0,0                               |
| DIZZINESS                             | 3                    | 4                  | 1,1,1,1                             | 1,0,2,2  | 1,1,0,1                           | 0,0,1,1                           |
| FATIGUE                               | 2                    | 2                  | 1,1                                 | 1,2  | 0,0                               | 0,1                               |
| FEELINGS OF UNEASINESS                | 1                    | 1                  | 1                                   | 2  | 1                                 | 0                                 |
| HEAD WARMING                          | 3                    | 13                 | 1,1,1,1,1,
1,1,1,1,1,
1,1,1   | 4,4,4,4,4,
4,4,4,4,4,
4,4,4  | 1,1,1,1,1,
1,1,1,1,1,
1,1,1 | 1,1,1,1,1,
1,1,1,1,1,
1,1,1 |
| HEADACHE                              | 2                    | 2                  | 1,1                                 | 2,3  | 0,1                               | 1,1                               |
| INSOMNIA                              | 1                    | 2                  | 1,1                                 | 2,0  | 1,0                               | 1,1                               |
| ITCHINESS ON UPPER BACK               | 1                    | 1                  | 1                                   | 0  | 0                                 | 0                                 |
| JAW PAIN/TEETH CLENCHING DURING SLEEP | 1                    | 1                  | 1                                   | 1  | 0                                 | 0                                 |
| LIGHTHEADEDNES S                      | 1                    | 1                  | 1                                   | 0  | 1                                 | 0                                 |
| POSITIONAL VERTIGO IN MRI             | 1                    | 1                  | 1                                   | 0  | 1                                 | 1                                 |

## Mass General Brigham Institutional Review Board Intervention/Interaction Detailed Protocol

|                                      |   |    |   |   |   |   |
|--------------------------------------|---|----|---|---|---|---|
| RASH (UPPER BACK)             | 1 | 1  | 1   | 1   | 1   | 1   |
| SEEING LIGHT DURING TREATMENT | 1 | 1  | 1   | 4   | 1   | 1   |
| SKIN REDDENING                |   |    | 1,1,1,1,1,
1,1,1,1,1,
1,1,1,1,1,
1,1,1,1,1,
1,1,1,1,1,
1,1 | 4,4,4,4,4,
4,4,4,4,4,
4,4,4,4,4,
4,4,4,4,4,
4,4 | 1,1,1,1,1,
1,1,1,1,1,
1,1,1,1,1,
1,1,1,1,1,
1,1 | 1,1,1,1,1,
1,1,1,1,1,
1,1,1,1,1,
1,1,1,1,1,
1,1 |
|                                      | 3 | 27 |   |   |   |   |
| Skin warming (forehead)       |   |    | 1,1,1,1,1
1,1,1,1,1
1,1,1,1,1
2,1,1,1,1
1,1                   | 4,4,4,4,4,
4,4,4,4,4,
4,4,4,4,4,
4,4,4,3,
4,4   | 1,1,1,1,1
1,1,1,1,1
1,1,1,1,1
1,1,1,1,1
1,1     | 1,1,1,1,1,
1,1,1,1,1,
1,1,1,1,1,
1,1,1,1,1,
1,1 |
| Stomach Discomfort            | 1 | 1  | 1   | 1   | 1   | 0   |
| Vivid Dreams                  | 2 | 2  | 1,1   | 2,2   | 1,1   | 1,1   |
| Vomiting                      | 1 | 1  | 1   | 0   | 1   | 0   |

## Assessments

### *Adverse Events Form*

The Adverse Events Form captures any adverse event (serious or otherwise) that the subject experiences while participating in the study. Events may occur during or outside of study procedures.

### *Altman Self-Rating Mania Scale (ASRM)*

The ASRM is a 5-item self-rated mania scale designed to assess the presence and/or severity of manic symptoms over the past 7 days. This scale will be administered as part of the pre-screening phase.

### *Barratt Impulsiveness Scale (BIS)*

The BIS is a 30-item measure of cognitive and motor impulsivity rated on a 4-point Likert scale (1 = rarely/never to 4 = almost always/always). It captures three factors: Motor Impulsiveness, Non-Planning Impulsiveness, and Attentional Impulsiveness. The BIS has demonstrated high internal consistency and validity across populations.

### *Behavior Rating Inventory of Executive Function – Adult Version (BRIEF-A)*

The BRIEF-A is a 75-item self-report scale to assess executive function. It consists of two indices: The Behavioral Regulation Index and the Metacognitive Index. The Behavioral Regulation Index measures inhibition, set shifting, control, and attention monitoring. The Metacognitive Index measures ability to initiate tasks, working memory, planning/organization ability, task monitoring, and organization. The BRIEF-A has demonstrated good internal consistency and validity across several clinical populations and non-clinical controls.

### *Concise Associated Symptom Tracking Irritability Scale (CAST-IRR)*

This instrument is a five item self-report that assesses irritability over the last 24 hours.

### *Clinical Global Impressions – Severity and Improvement (CGI-S, CGI-I)*

These two instruments are scored 1-7 by the clinician based on assessment of the subject's overall clinical status. They measure, based on history and scores on other instruments: (a) severity of impairment (CGI-S) and (b) clinical improvement (CGI-I).

### *Columbia Suicide Severity Rating Scale (C-SSRS)*

An instrument endorsed by the FDA for clinical trials. This instrument systematically tracks suicidal ideation and behavior (e.g., suicide attempts, wish to die, thoughts of suicide, plan, and intent).

*Concomitant Medications and Therapies Form*

This form records all ongoing medications, as well as other therapies, and will be completed at every study visit, including the screening visit, as a safety-monitoring tool.

*Iowa Gambling Task*

In this computerized task, participants play a game of chance in which they can win or lose fake money. Participants are presented with four cards and are asked to choose one. Their choice results in a gain or loss. Participants are given feedback on each choice. This task is designed to measure impulsivity.

*Delgado Gambling Task (IGT)*

In this computerized task, participants play a game of chance in which they can win or lose fake money. Participants are given a target number. They are then presented with a sequence of cards. Before each card is presented, participants are asked to guess whether the number on the next card will be higher or lower than the target number. They are then given feedback on their choice. This task is designed to measure reward-processing.

*I-7: Impulsiveness and Venturesomeness Questionnaire*

The I-7 is a self-report scale of 54 items and three subscales. Of the 54 items, 19 measure Impulsiveness, 16 measure Venturesomeness, and 19 measure Empathy. Answers are marked as “Yes” or “No.”

*Mini International Neuropsychiatric Interview (M.I.N.I)*

The M.I.N.I. is a short structured diagnostic interview, developed jointly by psychiatrists and clinicians in the United States and Europe, for DSM and ICD psychiatric disorders. With an administration time of approximately 15 minutes, it is designed to meet the need for a short but accurate structured psychiatric interview for clinical trials. According to researchers at the National Institute of Mental Health's (NIMH) Division of Clinical and Treatment Research, the M.I.N.I. is a fully validated and more time-efficient alternative to the Structured Clinical Interview for DSM Disorders (SCID). For the purposes of this study, we will only use modules related to mood, psychosis, and substance abuse.

*MOODS-SR – Last Week & Lifetime*

This 161-item self-report scale assesses manic-depressive symptoms. Participants are asked to answer “Yes” or “No” to each question. Subdomains measure Moods, Energy, Cognition, and Rhythmicity. Time frame is either lifetime or the last week, depending on scale used.

*MRI Safety Checklist*

This form identifies risk factors that may make MRI participation unsafe.

*New Immigrant Survey-Skin Color Scale (NIS-SCS)*

The NIS-SCS is an 11-point scale, ranging from zero to 10, with zero representing albinism, or the total absence of color, and 10 representing the darkest possible skin. The ten shades of skin color corresponding to the points 1 to 10 on the Massey and Martin Skin Color Scale are depicted in a chart, with each point represented by a hand, of identical form, but differing in color. The respondent never sees the chart. We gather this data for use as a potential covariate in analyses as skin color can affect absorption of NIR.

*Patient Health Questionnaire (PHQ-9)*

This nine-item self-report measure assesses the presence and severity of depressive symptoms over the past 14 days. This scale will be administered as part of the pre-screening phase.

*Perceived Blinding Questionnaire (PBQ)*

The PBQ is a self-report questionnaire to determine the degree to which the participant believes they are receiving active treatment or sham.

*Prior Treatment Log*

This form captures information regarding prior treatments for bipolar disorder or other mental health concerns.

*Systematic Assessment for Treatment Emergent Events (SAFTEE)*

The SAFTEE is a commonly used instrument originally developed by NIMH and adapted into a self-report instrument. The version of the scale that we plan to use is the same used by the multi-center, NIMH-sponsored CO-MED trial, and it examines in a systematic fashion all possible treatment-emergent side effects and probes specific adverse symptoms, including suicidal thoughts and behaviors, and self-injurious behavior.

*t-PBM Self-Report Questionnaire (TSRQ)*

An open-ended questionnaire focusing on potential inconveniences and discomforts from the t-PBM treatment.

*Young Mania Rating Scale (YMRS)*

This 11-item clinician-rated scale is used to assess the presence and severity of manic symptoms.

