**3. To test the effect of repeated t-PBM sessions on impaired decision making, in subjects with impulsivity due to BD**

*Hypothesis:* repeated t-PBM sessions on the R-dlPFC will significantly improve decision making – increase in net gain at the Iowa gambling task, decrease in Barratt Impulsiveness Scale (BIS) score at day 5 and follow-up visit relative to baseline, decrease in BRIEF-A score at day 5 and follow-up visit relative to baseline, and a decrease in I-7 Impulsiveness and Venturesomeness Questionnaire score at day 5 and follow-up visit relative to baseline.

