### **3. General Description of Study Design**

This is a single-blind study to test the neuropsychological and clinical effects of t-PBM with NIR in BD. For our primary aim of examining the effect of tPBM on CBF, the study is additionally sham-controlled. Twenty patients with a diagnosis of bipolar disorder, not currently in a depressive, manic, or mixed state episode, will undergo one sham and one NIR- t-PBM session on day 1 (within MRI scanner), and one daily NIR- t-PBM session from day 2 to 5. On day 5, the NIR t-PBM session will also occur in the MRI scanner. The fMRI scan will measure BOLD changes during sham t-PBM (day 1) and during NIR t-PBM (day 1 & 5), on R-dlPFC.

Impulsivity will be assessed by the BIS at pre-screen (for inclusion criteria), baseline, treatment day 5, and the follow-up visit; and by the gambling tasks at baseline, after the first NIR t-PBM (day 1), after the fifth NIR t-PBM (day 5), and at the follow-up visit. Other aspects of impulsivity and executive functioning will be assessed by the I-7 and BRIEF-A at baseline, day 5, and the follow-up visit. The MOODS-SR-Last Week will be administered at baseline, day 5, and the follow-up visit to assess change in mood, particularly hypomanic symptoms. At screening, subjects will complete the MOODS-SR Lifetime.

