t-PBM is not considered standard of care and is therefore an alternative treatment for bipolar disorder. Standard of care for bipolar disorder includes, but is not limited to, psychotherapy, medications (such as mood stabilizers, anti-depressants, or anti-psychotics), or device-based treatments (such as ECT). Information on standard of care for bipolar disorder will be provided to all subjects. Subjects may continue with their current treatment regimen throughout the study.

The MGH Brain Photobiomodulation Clinic (Director: [name] PhD) has historically served as a resource for subjects enrolled in t-PBM clinical trials who then wish to continue with specialized supervision. Study staff will offer access to the clinic to all subjects upon study completion.

Participants will be compensated \$125 for each of the following visits: Baseline, Treatment 1, Treatment 5, and Follow Up. For each of these visits, the participant receives \$25 for attending the appointment, \$50 for completion of the first gambling task, and \$50 for the completion of the second gambling task. Participants who complete all portions of the study will receive a total of \$500. Subjects who end study procedures prematurely will be compensated for all completed study procedures. Subjects will be mailed a check at the conclusion of their study participation.

While participants will always receive the full \$50 for completing each gambling task, they will be told that their real-world earnings are based on their performance on the gambling task. They will be told that the maximum amount of real-world money that they can earn in each task is \$50. Participants will be told that the better they do on the task, the closer they will get to earning the full \$50, and that their total earnings will be revealed at the final study visit. The purpose of these gambling tasks is to investigate various aspects of behavior, such as impulsivity and decision-making. In order for these tasks to effectively gather accurate data on these behaviors, it is crucial that the participants believe that the amount of money they earn is based on their decisions within the task. Upon completion of all study procedures, participants will be informed that they will receive the full \$50 for each of the eight gambling tasks that they completed.

This deception may result in increased frustration related to performance on the gambling tasks. This deception involves no more than minimal risk to the participants.

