## 9. Statistical Analysis

Preprocessing of MRI and fMRI data will be performed with the FreeSurfer software package, scripted in Bash. Slice-time correction, motion-correction, and co-registration of functional BOLD scans, Time of Repetition (TR), and participant will then be performed. BOLD signals will then be smoothed to a full-width half maximum (FWHM) of 3mm and z-scored at every voxel.

t-PBM related increase of BOLD percent signal change (PSC) averaged across all ROI voxels will be assessed during the first scanning session where the participant receives both sham and NIR over the R-dlPFC. PSC of t-PBM related increase in BOLD both during and after stimulation will be the dependent variable with the independent variable being the condition of t-PBM during the first session (sham vs. NIR).

BOLD signal will again be assessed during the 5th NIR session as a PSC across all ROI voxels in comparison with the BOLD PSC from the first NIR session to observe any BOLD changes after 5 NIR treatment sessions. The dependent variable will be the BOLD signal and the independent variable will be the timepoint: day 1 vs. after 5 sessions (day 5).

For both gambling tasks, the gambling task net gain score will be analyzed for changes from baseline to after treatment on day 1, baseline vs day 5, and baseline vs follow up. The BIS, BRIEF-A, and I-7 will be analyzed for changes from baseline to day 5 and follow up. Here, the dependent variable will be the gambling tasks' net gain scores, BIS, BRIEF-A, and I-7 total score. The independent variable is the timepoint baseline vs. day 5 (for the gambling tasks) and follow up. The MOOD-SR will also be analyzed for a decrease in impulsivity at each timepoint of baseline vs. day 5 and follow up. A General Mixed Models Regression will be used with time as a fixed effect and subject as a random effect.

Secondary analyses will also be performed for the BIS, BRIEF-A, I-7, MOOD-SR, SAFTEE, and TSRQ. Each scale and their respective subscales will be analyzed for specific changes at

each timepoint to better understand the effect t-PBM NIR has on the symptoms and presentation of BD. These additional analyses will also be helpful in assessing the initial safety profile of t-PBM in this psychiatric population.

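### Aim 3 reads a rise in Iowa gambling task net gain as an effect of t-PBM, but the design cannot separate it from practice over four feedback-driven runs

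*Combined protocol and SAP*

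**What the plan says.** Section 2, Aim 3 predicts that "repeated t-PBM sessions on the R-dlPFC will significantly improve decision making". The first outcome it lists is an "increase in net gain at the Iowa gambling task".

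Section 3 schedules impulsivity testing "by the gambling tasks at baseline, after the first NIR t-PBM (day 1), after the fifth NIR t-PBM (day 5), and at the follow-up visit". Section 5 agrees with that count: participants are to be paid in full "for each of the eight gambling tasks that they completed", which is two tasks at four visits. Section 5 also says participants are told that doing better brings them closer to the maximum payment, so that they are motivated to perform well.

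The Iowa entry under Assessments in Section 6 describes a choice among four cards, each choice ending in a gain or a loss, and adds: "Participants are given feedback on each choice".

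On control, Section 3 says: "For our primary aim of examining the effect of tPBM on CBF, the study is additionally sham-controlled". In Section 6, Treatment 1, the day 1 Iowa run comes at the end of the visit, after both the sham and the active stimulation. At Treatment 5 it comes after the fifth active session.

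Section 9 compares each later gambling score with baseline and states: "A General Mixed Models Regression will be used with time as a fixed effect and subject as a random effect".

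**The concern.** A participant who sits the same kind of task four times over a few weeks, sees the result of every choice and believes money depends on it has both the opportunity and the motive to improve. The plan has nothing that would show how much of any improvement comes from this. Sections 6 and 9 describe no alternate versions, no practice run before baseline, no untreated or sham series for this outcome, and no adjustment for repeated exposure. The randomised task order at baseline and follow-up decides only which of the two gambling tasks comes first within a visit.

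What is at stake is the conclusion of Aim 3. A significant rise in net gain would be reported as t-PBM improving decision making in bipolar disorder, when the same result could arise with no treatment effect. The ambiguity also runs the other way: fatigue or frustration at later runs could hide a real benefit.

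**Working it through.** **No figure to reproduce.** The plan gives no power, alpha or sidedness for Aim 3. Its only power statement (Section 9) concerns Aim 1.

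**Step 1: what differs between visits** (Sections 3 and 6).

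| Iowa run | Earlier Iowa runs | Active sessions so far |
|---|---|---|
| Baseline | 0 | 0 |
| Day 1 | 1 | 1 |
| Day 5 | 2 | 5 |
| Follow-up | 3 | 5 |

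Every planned contrast is a later row against the first row, so each sets treated and repeated against untreated and new.

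**Step 2: what the model estimates.** For participant i at visit j, the planned model is

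Y(ij) = mean + time(j) + subject(i) + error(ij).

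The contrast time(j) − time(baseline) equals treatment effect(j) + practice effect(j) + any other drift(j). There is one estimable quantity per visit and at least two unknowns. The two middle columns of the table are not proportional. An analyst could therefore separate them on paper by assuming a shape for the practice curve and for the persistence of treatment a week after the last session. The plan assumes neither, and the documents offer no basis for choosing.

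**Step 3: illustration of size.** Inputs: n = 20 (Sections 3 and 4); two-sided 0.05 and a paired t-test (my assumptions); zero treatment effect; practice gain d in SDs of the change score (assumed).

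- Critical value: t(0.975; 19 df) = 2.093.
- Noncentrality: d × √20 = d × 4.472.
- d = 0.2: 0.894, rejection 13.6%.
- d = 0.3: 1.342, rejection 24.7%.
- d = 0.5: 2.236, rejection 56.45%.

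Almost all of these rejections are in the favourable direction, where the nominal rate is 2.5%.

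**Step 4: the planned type of model.** A simulation (20,000 runs) of a random-intercept model with four visits, n = 20, correlation 0.5 between visits, and an assumed gain of 0.2 SD per repeat with no treatment effect gave a significant favourable contrast in 14% at day 1, 42% at day 5 and 75% at follow-up. At least one of the three was significant in 80%. With no practice gain, each contrast was significant in the favourable direction in about 2.5%. At correlation 0.5 the SD of a change is √(2 × (1 − 0.5)) = 1, so the day 1 gain is d = 0.2 and the 14% agrees with Step 3.

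**Step 5: why a sham arm is not the request.** In the same simulations, 10 against 10 with the same four runs kept the day 5 false-positive rate at about 5% at every practice gain tried. Power is the obstacle. By normal approximation at d = 0.5 on the change score, 10 per arm gives Φ(0.5 × √5 − 1.96) = Φ(−0.84), about 20%. Reaching 80% needs 2 × (1.96 + 0.842)² / 0.5² = 62.8, or about 63 per arm.

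**The case against.** **The mechanism is not fully described.** The Iowa entry calls the task a game of chance. It does not describe a fixed set of better and worse cards, or say that the layout is the same at each visit. This stands: a reader might infer that identical versions are used, and the documents do not show it. The aliasing does not depend on it, however. If choices could not affect payoff, net gain could not measure decision making either, and Section 5 ties the announced earnings to doing well.

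**The direction of drift is assumed.** The day 1 run follows a scan of about 75 minutes and the Delgado task in the scanner. Section 5 warns that the deception may increase frustration, and Section 7 mentions boredom. This also stands: the documents do not show that practice dominates, only that it cannot be separated from treatment.

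**The percentages are generic.** They would be the same for any uncontrolled series of 20 with a shift of that size. That is correct, and they should not be read as this trial's false-positive rate.

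**The limits are already disclosed.** Section 3 attaches the sham control to the blood-flow aim, and Section 7 says the study is not geared to testing a treatment. That softens the point, but Aim 3 keeps its causal wording. The questionnaires under Aim 3 are uncontrolled too; the Iowa task is singled out because feedback and incentive add a specific route to improvement.

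**Conclusion.** The point holds as a limit on what Aim 3 can conclude. The Iowa contrasts cannot separate t-PBM from practice, and the wording of the aim claims that they can. This rests on the visit schedule, the single treated group and the time-only model, all stated in the documents.

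Its size is not known. About 25% or 56% rejection follows only if practice is worth 0.3 or 0.5 SD of the change score, in a two-sided paired t-test at 0.05 with 20 participants. If practice is negligible and nothing else drifts, there is no inflation.

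Three stronger readings are not supported. The documents do not show that practice will raise scores, only that it could. They do not show that the layout is repeated. Nor should a reader infer that Aim 1 is free of a similar problem because it has a sham: Section 6, Treatment 1 gives sham before active in a fixed order, so that comparison is tied to time within the session.

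The change is worth making because it is cheap and alters what may be concluded. Layouts have to be in place before testing, since the separation cannot be recovered in analysis.

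**What to change.** 1. In Section 6, specify a different card and payoff layout for each of the four Iowa visits, with version order counterbalanced across participants. If this is already done, say so. It removes memory of a particular layout.
2. Learning how to approach the task would remain. So, in Section 2 (Aim 3) and Section 9, restate the Iowa outcome and its conclusion as change over time in an uncontrolled series, and note that practice and treatment are not separable.

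The cost is minor re-programming of a computerised task, a little between-version variance (which counterbalancing keeps from lining up with visit), and a more modest Aim 3 claim. No extra participants or visits are needed.
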